7.4.5.8 Change in HRQOL as Measured by the EORTC QLQ-30 and EQ-5D-5L

The EORTC QLQ-30 and EQ-5D-5L test results will be summarized separately by treatment group, parameter, and visit based on the mITT analysis set. For EORTC QLQ-30, results for global health status, each of the 5 functional scales (physical, role, emotional, cognitive, and social functioning), and each of the 8 symptom scales (fatigue, nausea and vomiting, pain, dyspnea, insomnia, appetite loss, constipation, and diarrhea) will be summarized. The scores for global health status, functional scales, and symptom scales will be calculated and standardized using the methods described in *The EORTC QLQ-C30 Scoring Manual* (3rd Edition) (Fayers 2001). For EQ-5D-5L, results for overall health, each of the 5 dimensions (mobility, self-care, usual activities, pain/discomfort, and anxiety/depression), and the visual analogue scale will be summarized.

Descriptive statistics will be presented for observed values and changes from baseline by parameter at each visit and endpoint (last observation carried forward [LOCF] up to the 30-day Safety Follow-up Visit) where the questionnaires were scheduled to be collected per the clinical study protocol. Change from baseline in each parameter will be analyzed using a mixed model for repeated measures (MMRM). The model will include treatment, visit (restricted up to the 30-day Safety Follow-up Visit), and treatment-by-visit interaction as fixed effects and baseline as covariate. An unstructured covariance structure will be used to model the between- and within-participant errors.

The Kenward-Roger method will be used to estimate the degrees of freedom. Treatment least square means (LSMs) will be estimated within the framework of the MMRM using type 3 sums of squares. Differences in LSM between treatment groups (and associated standard errors and 95% CI) will be used for statistical inference. The LSM difference, standard error, and 95% CI will be reported for each parameter and visit.

A by-participant listing of all EORTC QLQ-30 and EQ-5D-5L results will be provided.

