4 STUDY DESIGN

4.1 Overall Design

This is a Phase 3, multi-center, randomized, double-blind, placebo-controlled study comparing the activity of tamibarotene plus azacitidine to placebo plus azacitidine as first line of therapy in

RARA-positive patients with newly diagnosed HR-MDS. Enrollment in countries in North America and Europe and in Israel is planned.

At the Pre-screening Visit, blood samples will be collected and sent to the Almac Diagnostics Laboratory for assessment of RARA biomarker to determine study eligibility. Pre-screening assessments for the RARA biomarker will be performed within 45 days of Cycle 1 Day 1 and screening assessments for all other eligibility criteria will be performed within 30 days of Cycle 1 Day 1.

Patients will be randomized 2:1 to receive either tamibarotene plus azacitidine or placebo plus azacitidine. Randomization will be stratified by the IPSS-R risk group (Intermediate, High, and Very High Risk) and by geographical region (North America, Western Europe, and Israel versus Eastern Europe); block randomization with a block size of 6 will be used.

Response will be assessed by the investigator per the modified IWG MDS criteria (Cheson 2006). Bone marrow aspirates will be collected to measure response on Day 1 of Cycles 2 and 4, followed by every third cycle (7, 10, 13, etc.), with bone marrow aspirates collected at other times as clinically determined based upon clinical findings or changes in peripheral blood counts. Following the response assessment on Day 1 of Cycle 7, those in CR may have the frequency of bone marrow aspirates for response assessment reduced to every 6 cycles.

Patients will undergo response and safety evaluations throughout their study participation as detailed in the Schedule of Activities (SoA; Section 1.3). Patients may continue to receive study drug until experiencing an unacceptable toxicity, disease progression (including transformation into AML), relapse, decision to pursue post-remission therapy (such as HSCT) or an alternative anticancer therapy, patient withdraws consent, or the investigator determines it is in the best interest of the patient to discontinue study drug.

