Time to initial response, defined as the duration from the date of randomization to the date of the first documented evidence of CR, PR, mCR, or HI as determined by the investigator per the modified IWG MDS criteria (Cheson 2006).

Time to initial response will be summarized descriptively for the 2 treatment groups.

EFS

EFS, defined as the time from the date of randomization to the date of transformation to AML or death due to any cause, whichever occurs first.

Kaplan-Meier estimation of median EFS and 95% CI will be presented by treatment group. The stratified log rank test will be used to analyze the difference in EFS between treatment groups.

Change in HRQOL

EORTC QLQ-30 and EQ-5D-5L test results will be summarized separately by treatment group, parameter, and visit. For EORTC QLQ-30, results for global health status, each of the five functional scales (physical, role, emotional, cognitive, and social functioning), and each of the eight symptom scales (fatigue, nausea and vomiting, pain, dyspnea, insomnia, appetite loss, constipation, and diarrhea) will be summarized. The scores for global health status, functional scales and symptom scales will be calculated and standardized using the methods described in The EORTC QLQ-C30 Scoring Manual (3rd Edition) (Fayers 2001). For EQ-5D-5L, results for overall health and each of the 5 dimensions (mobility, self-care, usual activities, pain/discomfort, and anxiety/depression) will be summarized.

Descriptive statistics will be presented for observed values and changes from baseline by parameter at each visit where the questionnaires were scheduled to be collected per the clinical study protocol. Change from baseline in important parameters will be analyzed using MMRM. The model will include treatment, visit, and treatment-by-visit interaction as fixed effects and baseline as covariate. An unstructured covariance matrix will be used to model the between- and within-patient errors.

The Kenward-Roger method will be used to estimate the degrees of freedom. Treatment least squares means (LSMs) will be estimated within the framework of the MMRM using type 3 sums of squares. Differences in LSM between treatment groups (and associated standard errors and 95% CI) will be used for statistical inference. The LSM difference, standard error, and 95% CI and will be reported for each parameter and visit.

A by-patient listing of all EORTC QLQ-30 and EQ-5D-5L results will be provided.

Safety Analyses

Adverse Events

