6.3.2 Method of Assigning Participants to Treatment Groups and Blinding

The study is double blinded, and randomization will be performed on Cycle 1 Day 1 using an interactive response system. Participants can be randomized earlier than Cycle 1 Day 1, but within 72 hours of the first dose of study drug, to accommodate operational needs.

Approximately participants with HR-MDS will be randomly assigned to study drug. Participants will be randomized 2:1 to receive either tamibarotene plus azacitidine or placebo plus azacitidine. Randomization will be stratified by the IPSS-R risk group (Intermediate, High, and Very High Risk). In addition, stratification of analyses by geographical region (North America, Western Europe, plus Israel, and Eastern Europe) will be performed, as there may be differences in available supportive care treatments and in access to subspecialty consultants and specialized hospital care among these regions. All participants, investigators, pharmacist(s) performing drug preparation, and site staff will be blinded to treatment assignment.

Personnel responsible for the bioanalysis of the tamibarotene concentrations in plasma will be provided with the randomization code in order to identify samples for analysis. The results will not be shared with the sponsor until the study is unblinded.

In addition, at the time of CR futility analysis, preliminary PK analysis will be performed by designated contract research organization (CRO), and the limited personnel from the CRO will have access to the unblinded PK data to build the population PK model.

To maintain study integrity, OS data will be kept blinded for Syros at the time of CR final analysis and beyond. Only 1 independent SAS programmer at Syros, who does not directly support this study, will have access to the OS data; the OS data will be stored in a separate study folder and can only be accessed by the independent SAS programmer. Further details will be outlined in the Blinding Maintenance Plan.

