The primary endpoint will be tested at a full alpha level of 2.5%. To control the overall Type I error rate of the primary and key secondary endpoints, hierarchical testing will be performed in the following order: (1) primary endpoint; (2) key secondary endpoint. If hypothesis testing of the primary endpoint is rejected, the key secondary endpoint will be tested at the full alpha level of 2.5%; otherwise, the testing will be stopped. Secondary and exploratory efficacy endpoints will be tested using a two-sided, 5% significance level, and two-sided 95% CIs will be reported when appropriate, unless otherwise specified. P-values will be rounded to 4 decimal places. P-values less than 0.0001 will be displayed as "<0.0001"; p-values greater than 0.9999 will be displayed as ">0.9999".

When applicable, analyses will be stratified by IPSS-R risk group (Intermediate, High, and Very High Risk) and by geographical region (North America, Western Europe, plus Israel, and Eastern Europe).

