7.4.3 Primary Efficacy Endpoint Analysis Methods

7.4.3.1 Primary Estimand Analysis for CR

The final analysis of CR is planned for the time when the first approximately **CCI** randomized participants out of the planned **CCI** participants have completed the Cycle 7 Day 1 response assessment or discontinued treatment, whichever comes first.

The primary endpoint is CR achieved by Cycle 7 Day 1, as determined by the investigator per the modified IWG MDS criteria (Cheson 2006). There is expected to be a high correlation between CR achieved by Cycle 7 Day 1 and CR achieved at any time (Silverman 2006; VIDAZA UPSI), and therefore, the same effect size and other design assumptions are justified in the hypothesis testing below. The objective is to demonstrate the superiority of tamibarotene plus azacitidine compared to placebo plus azacitidine in CR in RARA-positive newly diagnosed HR-MDS participants.

The null hypothesis (H₀) to be tested is:

In RARA-positive participants with newly diagnosed HR-MDS, CR rate for participants in the tamibarotene plus azacitidine treatment group is the same as the CR rate for participants in the placebo plus azacitidine treatment group.

The alternate hypothesis (H_A) to be tested is:

In RARA-positive participants with newly diagnosed HR-MDS, CR rate for participants in the tamibarotene plus azacitidine treatment group is higher than the CR rate for participants in the placebo plus azacitidine treatment group.

The following analyses will be conducted separately:

- [1] Primary analysis of primary estimand (investigator response in mITT analysis set)
- [2] Sensitivity analysis of primary estimand (investigator response in ITT analysis set)
- [3] Sensitivity analysis of primary estimand (investigator response in PP analysis set)

The CR rate and 95% exact binomial CIs based on the Clopper-Pearson exact method will be calculated by treatment group.

Confidential

Syros Pharmaceuticals, Inc. SY-1425-301

The CR rate will be analyzed using the Cochran-Mantel-Haenszel (CMH) test to compare the 2 treatment groups with a 1-sided 2.5% level of significance. The strata for the test will be those used for stratified randomization, with potential pooling of strata if there is insufficient information in any stratum; the pooling strategy is specified in Section 7.4.2. The point estimate of the difference of the proportions for CR rate between the 2 treatment groups will be provided along with its 95% CI.

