7.4.4 Key Secondary Efficacy Endpoint Analysis Methods

The key secondary endpoint is the OS, defined as the time from the date of randomization to the date of death from any cause. The objective is to demonstrate the superiority of tamibarotene plus azacitidine compared to placebo plus azacitidine in OS in RARA-positive newly diagnosed HR-MDS participants.

The final analysis of OS will occur when a total of CCI death events is reached, which is approximately 70 months following the enrollment of the first participant.

The H₀ to be tested is:

In RARA-positive participants with newly diagnosed HR-MDS, OS for participants in the tamibarotene plus azacitidine treatment group is the same as the OS for participants in the placebo plus azacitidine treatment group.

The H_A to be tested is:

In RARA-positive participants with newly diagnosed HR-MDS, OS for participants in the tamibarotene plus azacitidine treatment group is superior to the OS for participants in the placebo plus azacitidine treatment group.

The primary analyses of OS will be based on the ITT analysis set.

OS is defined as the time from the date of randomization to the date of death due to any cause. Participants who do not die at the time of a data cutoff date (interim and/or final) will be censored at the last date the participant is known to be alive or at the analysis cutoff date, whichever is earlier.

The distribution of OS will be estimated for each treatment group using Kaplan-Meier methodology and compared between the 2 treatment groups using the log-rank test stratified by IPSS-R risk group (Intermediate, High, and Very High Risk) and by geographical region (North America, Western Europe, plus Israel, and Eastern Europe) at 1-sided 2.5% significance level.

The hazard ratio and corresponding 95% CI between the 2 treatment groups will be estimated using the stratified Cox proportional hazards model with the same stratification factors that are used for the stratified log-rank test. For both the stratified log-rank test and the stratified Cox proportional hazards model, the strata will be those used for stratified randomization, with potential pooling of strata specified in Section 7.4.2.

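### The HRQOL mixed model omits IPSS-R risk group and region, the strata used in the main tests of CR, OS, TI, ORR and EFS

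*SAP*

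**What the plan says.** SAP 7.4.5.8 compares the arms on change from baseline in each EORTC and EQ-5D-5L parameter with a mixed model for repeated measures. The fixed part is treatment, visit "and treatment-by-visit interaction as fixed effects and baseline as covariate". Protocol 9.4.4 gives the same list: "The model will include treatment, visit, and treatment-by-visit interaction as fixed effects and baseline as covariate". The least squares mean differences and their confidence intervals are the stated basis for inference.

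Both documents also carry a general rule. SAP 7.1.1 reads: "When applicable, analyses will be stratified by IPSS-R risk group (Intermediate, High, and Very High Risk) and by geographical region". Protocol 9.4.1 has the equivalent line. Neither says which analyses it applies to.

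On the design, protocol 4.1 says: "Randomization will be stratified by the IPSS-R risk group (Intermediate, High, and Very High Risk) and by geographical region". SAP 6.1 agrees. SAP 6.3.2 puts it differently: it names IPSS-R for randomization and then continues "In addition, stratification of analyses by geographical region". Protocol 6.3 has the same wording.

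The main tests use the factors. For CR, SAP 7.4.3.1 says: "The strata for the test will be those used for stratified randomization". For OS, SAP 7.4.4 has the arms "compared between the 2 treatment groups using the log-rank test stratified by IPSS-R risk group" and by region. TI and ORR use a stratified CMH test, and EFS a log-rank test stratified by both factors.

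**The concern.** DOCR, duration of overall response, time to CR and time to initial response are only estimated or described by arm. Among the secondary efficacy endpoints with a planned between-arm inference, HRQOL is therefore the only one whose main analysis names no stratification.

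Two things are at stake. One is precision. Stratified randomization removes most between-stratum variation from the treatment difference, but a model without the strata still counts that variation as residual error, so the reported standard error is too large whenever the strata predict the outcome. The other is pre-specification. One programmer could follow the term list and another the general rule, and they would report different differences and intervals for the same endpoint.

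**Working it through.** **Text check**

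| Comparison | Place in SAP | Strata |
|---|---|---|
| CR | 7.4.3.1 | Randomization strata (CMH) |
| OS, main test | 7.4.4 | IPSS-R and region |
| TI, ORR | 7.4.5.1, 7.4.5.2 | Stratified CMH |
| EFS, main test | 7.4.5.7 | IPSS-R and region |
| HRQOL | 7.4.5.8 | None in the term list |

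**Inputs for the size of the effect**

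- Two-sided 5% level for secondary endpoints: SAP 7.1.1, so z = 1.96.
- Levels: IPSS-R 3, region 2 (protocol 4.1). Main effects cost (3 − 1) + (2 − 1) = 3 degrees of freedom.
- R² is the share of residual variance, after baseline, that the strata explain. This is an assumption: the documents give no HRQOL variance, effect size or R². The range starts at zero.
- The plan states no HRQOL power or sample size, so there is no figure of its own to reproduce.

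**Formulas** (strata balanced between arms by the randomization)

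- Planned SE / adjusted SE = 1/√(1 − R²)
- True two-sided type I error of the planned test = 2·[1 − Φ(1.96/√(1 − R²))]
- Power of the planned test, for an effect that the adjusted model detects with 80% power = Φ(1.96 + 0.8416 − 1.96/√(1 − R²))

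Example at R² = 0.05: 1/√0.95 = 1.026; type I error = 2·[1 − Φ(2.011)] = 0.044; power = Φ(2.802 − 2.011) = 78.5%.

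| Assumed R² | SE ratio | Type I error | Power |
|---|---|---|---|
| 0 | 1.000 | 0.050 | 80.0% |
| 0.02 | 1.010 | 0.048 | 79.4% |
| 0.05 | 1.026 | 0.044 | 78.5% |
| 0.10 | 1.054 | 0.039 | 76.9% |
| 0.20 (outer case) | 1.118 | 0.028 | 72.9% |

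**Simulation check.** A single-visit analysis of covariance with complete data was simulated with 190 patients (the number in protocol 9.4.2), 2:1 allocation, blocks of 6 within six strata, assumed stratum shares and 6,000 runs per setting.

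| Assumed R² | SE ratio | Type I error, planned | Type I error, adjusted |
|---|---|---|---|
| 0 | 1.000 | 0.046 | 0.045 |
| 0.05 | 1.026 | 0.050 | 0.054 |
| 0.10 | 1.054 | 0.039 | 0.048 |
| 0.20 | 1.119 | 0.028 | 0.051 |

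Monte Carlo error on the rates is about 0.003. The SE ratios match the formula. The conservatism is clear at R² of 0.10 and above; at 0.05 it is too small to separate from simulation noise.

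**The case against.** The best defence is that the general rule already covers the model. Neither document gives an order of precedence, and the rule does real work elsewhere: the TI and ORR sections call for a stratified CMH test without naming strata. That much stands, so the text cannot be said to settle on omission. But those sections at least use the word stratified, whereas the HRQOL section lists its terms and has no such word. The rule does not add the factors to that list.

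It is also fair that the planned analysis is valid, that baseline of the same score may already carry most of what IPSS-R and region would explain, and that no claim in the testing hierarchy depends on HRQOL. All of this stands, and it limits the weight of the point.

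Three stronger readings are tempting, and the documents do not support them.

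- **That every other between-arm comparison is stratified.** It is not. OS sensitivity analysis 1 is an unstratified log-rank test with a treatment-only Cox model. The RMST comparisons for OS and EFS, the IPCW analysis and the logistic model for the RARA cutoff (SAP 7.4.6.8) name no strata.
- **That IPSS-R predicts dropout, so including it protects the missing-at-random assumption.** Neither document gives dropout or missing HRQOL data by IPSS-R group.
- **That the omission risks false positives.** The error runs the other way.

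**Conclusion.** The point holds as a low-severity improvement. The HRQOL model leaves out two factors that the main efficacy tests use, and the general rule leaves their place in it unsettled. The cost is a reported standard error 0 to 5.4% above the adjusted one for an assumed R² of 0 to 0.10, and a test run at a true level of 0.050 down to 0.039. The gain from adjustment may be nil.

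The type I error figures rest on both factors being strata of the randomization. If region is only an analysis stratum, as protocol 6.3 and SAP 6.3.2 can be read, its share would be ordinary lost precision, with the test at its nominal level; the standard error ratio would be about the same. The figures also come from a single-visit approximation with complete data, not from the full repeated-measures model.

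**What to change.** In SAP 7.4.5.8, add IPSS-R risk group (3 levels) and geographical region (2 levels), as assigned at randomization, as fixed effects, and apply the Section 7.4.2 pooling rule if a level is sparse. Record the departure from protocol 9.4.4 in SAP Section 8, since SAP Section 4 requires such changes to be explained. If the sponsor prefers to leave the factors out, one sentence should say so and why.

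The cost is a few words, a change entry and about 3 degrees of freedom. The six crossed cells of Section 7.4.2 would cost 6 − 1 = 5 instead; the text should say which form is meant. The same edit should reconcile the two descriptions of region, because the values assigned at randomization exist for region only if it was a randomization factor.

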7.4.5.9 Supplementary Estimand Analyses for Secondary Efficacy Endpoints

The supplementary estimand of secondary efficacy endpoints are DOCR and time to CR with CR achieved at any time, as determined by the investigator per the modified IWG MDS criteria (Cheson 2006).

The analysis will be performed using the same statistical methodologies as applied to the analysis for DOCR and time to CR with CR achieved by Cycle 7 Day 1 for participants in the mITT Analysis Set as described in Section 7.4.5.3 and Section 7.4.5.5.

7.4.6 Exploratory Efficacy Endpoint Analysis Methods

7.4.6.1 Cytogenetic Complete Remission

The cytogenetic CR rate as determined by the investigator per the modified IWG MDS criteria (Cheson 2006) will be analyzed using the same statistical methodologies as applied to the primary efficacy endpoint for participants in the mITT Analysis Set with a chromosomal abnormality at baseline, as described in Section 7.4.3.1. A by-participant listing of the derived efficacy data used for determining cytogenetic CR rate will be provided.

7.4.6.2 *Molecular Response*

Analysis of molecular response will be detailed in a separate document and is outside the scope of this SAP.

7.4.6.3 Transfusion Requirement

Transfusion requirement will be listed and summarized as described in Section 7.3.8.

7.4.6.4 Consolidation with Allogeneic HSCT Rate

The number and percentage of participants treated and not treated with allogeneic HSCT, along with 95% exact binomial CIs based on Clopper-Pearson exact method, will be summarized by treatment group for the mITT Analysis Set.

7.4.6.5 Complete Remission and Genetic Mutations and/or Gene Expression Markers

Any additional analyses of CR and genetic mutations and/or gene expression markers at baseline, at time of response, and loss of response will be detailed in a separate document and are outside of the scope of this SAP. All biomarker data that are collected in the clinical database will be listed.

